2.3 Trial Objectives

Primary: To determine the efficacy, safety, and dose and regimen of tolvaptan in pediatric heart failure patients with volume overload

Secondary: To determine the pharmacokinetics and pharmacodynamics of tolvaptan when administered to pediatric heart failure patients with volume overload

3 Trial Design

3.1 Type/Design of Trial

This is a multicenter, open-label, uncontrolled, dose-titration trial. In this trial, an ascending dose regimen where administration is started at a low dose is employed to ensure the safety of subjects. A basic trial design schematic is shown in Figure 3.1-1. After completion of a screening examination, subjects will be hospitalized prior to the evening meal on 3 days before start of tolvaptan administration. Tolvaptan administration will be started at 0.05 mg/kg/day, and subjects with sufficient increase in urine volume will continue administration at 0.05 mg/kg/day for 3 days. For subjects whose urine volume does not sufficiently increase, the dose may be increased to 0.15, 0.3, or 0.5 mg/kg/day according to the specification. In that case, the dose should be decided for each individual subject to obtain sufficient increase in urine volume, and administration at the decided dose will be continued for 3 days. When the dose is increased to 0.5 mg/kg/day, administration at 0.5 mg/kg/day should be continued for 3 days. After final tolvaptan administration, subjects will continue to be hospitalized for 2 days to undergo monitoring of condition. Subjects will also undergo the follow up 5 to 7 days after final tolvaptan administration.

[figure not shown]

Figure 3.1-1

Basic Trial Design Schematic

3.2 Trial Treatments

3.2.1 Dose and Regimen

Subjects will take tolvaptan 1% granules or tolvaptan 15 mg tablet with water once daily after breakfast.

The initial dose of tolvaptan will be 0.05 mg/kg/day. From the second day of the treatment period and onward, if necessary the dose may be increased to 0.15, 0.3, or 0.5 mg/kg/day according to the rules specified in [Section 3.2.2](#), and then the dose decided for each individual subject will be administered for 3 days. The dose of tolvaptan 1% granules to be administered will be determined depending on the subject's body weight on the day before start of tolvaptan administration; however, the maximum dose is 15 mg/day even if the calculated dose exceeds 15 mg/day. For administration at the maximum dose of 15 mg, tolvaptan 15-mg tablet may be administered in place of tolvaptan 1% granules. If the investigator or subinvestigator judges that there are an excessive aquaresis or safety concerns of subjects, the dose may be reduced (see [Section 3.2.3](#)). For subjects who need to continue treatment after 3-day administration at the dose decided individually, extended treatment for up to 4 days is allowed if the aim is to collect data on administration for up to 7 days and if the investigator or subinvestigator considers the safety of subjects to be ensured (including ensuring safety by dose reduction) (see [Section 3.2.4](#)). The dose, the date and time of administration, and the reason for dose reduction (for dose reduction, see [Section 3.2.3](#)) will be recorded in a source document and a case report form (CRF).

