In the dose-ranging trial of tolvaptan in adult heart failure patients with volume overload (Trial 156-03-001), tolvaptan was administered at 15 mg/day, 30 mg/day, or 45 mg/day, and urine volume was increased with an increase in dose. For a decrease in body weight, on the other hand, no difference was noted between the 3 doses. This finding demonstrated that a dose of 15 mg/day was sufficient to obtain clinical effects. As a result, the approved dose of tolvaptan for adult heart failure patients with volume overload was determined to be 15 mg/day. The maximum dose in pediatric heart failure patients (0.5 mg/kg/day) is equivalent to 30 mg/day (adults with a body weight of 60 kg) in adult heart failure patients. This dose is sufficient to obtain an aquaretic effect even the effect in pediatric heart failure patients is as weak as around half of that in adults. In the dose-ranging trial (Trial 156-03-001), 7-day repeated administration of placebo or tolvaptan at 15 mg/day (0.25 mg/kg/day for adults with a body weight of 60 kg), 30 mg/day (0.5 mg/kg/day for adults with a body weight of 60 kg), or 45 mg/day (0.75 mg/kg/day for adults with a body weight of 60 kg) resulted in thirst with an incidence of 10.3% in the placebo group, 21.4% in the tolvaptan 15 mg/day group, 27.3% in the tolvaptan 30 mg/day group, and 53.6% in the tolvaptan 45 mg/day group, showing the higher incidence of AEs associated with the pharmacological action of tolvaptan in the 45 mg/day group. It is unlikely that tolvaptan therapy will pose safety issues when its maximum dose is set at 30 mg/day (equivalent to 0.5 mg/kg/day in children). The dose of

0.5 mg/kg/day is equivalent to the upper limit on the dose of tolvaptan specified in the Clinical Guideline for Medical Treatment of Pediatric Heart Failure.

Therefore, a trial of tolvaptan using an ascending dose regimen within the range of 0.05 to 0.5 mg/kg/day can provide information about its appropriate dose and regimen in pediatric heart failure patients.

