3.2.2 Increasing the Dose of Tolvaptan

Tolvaptan should be administered according to the following procedure. Daily urine volume should be assessed as “insufficient increase in urine volume” when it is less than 150% of that for the pretreatment observation period (1 day before start of tolvaptan administration), and “sufficient increase in urine volume” when it is at least 150%.

- 1) Tolvaptan administration will be started at 0.05 mg/kg/day, and administration at 0.05 mg/kg/day will be continued for 2 days.
- 2) For subjects with sufficient increase in urine volume on Day 1 or Day 2 of treatment, administration at 0.05 mg/kg/day will be continued for 3 days. For subjects with an insufficient increase in urine volume on Day 1 and Day 2 of treatment, the dose will be increased to 0.15 mg/kg/day on Day 3.
- 3) If a sufficient increase in urine volume is observed following 2-day administration at 0.15 mg/kg/day on Day 3 or Day 4 of the treatment period, administration at 0.15 mg/kg/day will be continued for 3 days. For subjects with an insufficient

increase in urine volume on Day 3 and Day 4 of the treatment period, the dose will be increased to 0.3 mg/kg/day on Day 5.

- 4) If a sufficient increase in urine volume is observed following 2-day administration at 0.3 mg/kg/day on Day 5 or Day 6 of the treatment period, administration at 0.3 mg/kg/day will be continued for 3 days. For subjects with an insufficient increase in urine volume on Day 5 and Day 6 of the treatment period, the dose will be increased to 0.5 mg/kg/day on Day 7, and administration at 0.5 mg/kg/day will be continued for 3 days.

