3.2.3 Reducing the Dose of Tolvaptan

If symptoms associated with excessive aquaresis such as persistent sensation of thirst, dehydration, and hypernatremia are observed or there are safety concerns in subjects, at a discretion of the investigator or subinvestigator, the dose may be reduced only to the next lower dose. In that case, however, the dose of conventional diuretics should not be changed. If the dose of tolvaptan needs to be reduced before completion of 3-day administration at the same dose, it should be administered at the reduced dose for 3 days. If the dose of tolvaptan needs to be further reduced after dose reduction to the next lower dose, the subject will be judged to have a problem with tolerability to tolvaptan and should be withdrawn from the trial.

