3.2.4 Extended Treatment With Tolvaptan

Patterns of treatment with tolvaptan including extended treatment are shown in Figure 3.2.4-1. If the investigator or subinvestigator judges that the safety of subjects can continue to be ensured (including ensuring safety by dose reduction) after 3-day administration at the dose decided according to the specification for increasing the dose of tolvaptan (see [Section 3.2.2](#)), administration at that dose may be continued for up to 4 days (for up to 7 days in total).

In the case of an extended treatment with tolvaptan at reduced dose, the total number of administration days should be up to 7 days, which consists of “the days of administration at the dose just before the dose requiring reduction”, “the days of administration at the dose requiring reduction” and “the days of administration at the dose reduced to the next lower dose” (see examples of dose reduction in Figure 3.2.4-1).

[figure not shown]

Figure 3.2.4-1 Patterns of Treatment With Tolvaptan Including Extended Treatment

In principle, tolvaptan will be administered while increasing its dose every 2 days, and then, administered at the dose decided for each individual subject for 3 days. If the dose needs to be reduced before completion of 3-day administration, the dose may be reduced only once. The reduced dose should be regarded as the dose decided for each individual subject, and tolvaptan should be administered at the dose for 3 days. The duration of extended treatment at the reduced dose will be limited.

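### The 15 mg/day cap makes the 0.3 and 0.5 mg/kg steps the same amount from 50 kg, so the increase, reduction and dose-label rules between those steps have no effect on what is given

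*Protocol*

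**What the plan says.** Protocol 3.2.1, repeated in the synopsis and in SAP 3.2.1, starts every child at 0.05 mg/kg/day and says that "if necessary the dose may be increased to 0.15, 0.3, or 0.5 mg/kg/day". The amount is fixed from a single weight, "depending on the subject's body weight on the day before start of tolvaptan administration", and then limited: "however, the maximum dose is 15 mg/day even if the calculated dose exceeds 15 mg/day".

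The rules that move a child between doses are written in steps:

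- **Increase (Protocol 3.2.2, SAP 3.2.2).** If daily urine volume stays below 150% of the pretreatment value on Days 5 and 6 at 0.3 mg/kg, "the dose will be increased to 0.5 mg/kg/day on Day 7, and administration at 0.5 mg/kg/day will be continued for 3 days".
- **Reduction (Protocol 3.2.3, SAP 3.2.3).** For excessive aquaresis or another safety concern, at the investigator's discretion, "the dose may be reduced only to the next lower dose". If more is needed after that, "the subject will be judged to have a problem with tolerability to tolvaptan and should be withdrawn from the trial".
- **Discontinuation (Protocol 3.8.3.1, item 6).** Treatment stops if a reduction of two or more steps is needed.
- **Evaluation dose (Protocol 7.4, SAP 5.7).** This is the step at which urine volume responded, or 0.5 if that step was reached without response. A reduction before three days are complete moves it to the lower step.
- **Dose label in the analyses (SAP 8.3 and 10).** By-dose results and plasma concentrations are grouped by the mg/kg class entered in the CRF.

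No text found in either document says what an increase or a reduction means for a child already at the cap, and the eligibility criteria set no upper weight limit.

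**The concern.** The step rules assume that each step is a different amount. The cap breaks that assumption for the heaviest children. If the two top steps are both 15 mg, a site following the text records an increase on Day 7 that did not happen. A site reducing from nominal 0.5 to nominal 0.3 keeps giving the amount that raised the concern, and has used the only reduction allowed.

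Two things are at stake. The first is an effective dose reduction within the trial for these children. The second is the dose label. Dose and regimen is part of the primary objective, and the efficacy, safety and PK tables by dose would show identical 15 mg exposure under two mg/kg headings.

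**Working it through.** **Inputs.** Cap 15 mg/day; steps 0.05, 0.15, 0.3 and 0.5 mg/kg/day; one pretreatment weight for all steps (all Protocol 3.2.1). Age 6 months to under 15 years with no weight ceiling (3.4.2, 3.4.3). At most 24 children in the 7 to under 15 years group, out of 60 planned (3.3.1).

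**The plan's own conversion.** Protocol 2.2 equates 0.5 mg/kg/day with 30 mg/day at 60 kg: 0.5 × 60 = 30. Its other conversions also reproduce: 15/60 = 0.25 and 45/60 = 0.75 mg/kg.

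**Weight at which each step reaches the cap** = 15 / step:

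- 0.5 mg/kg: 15/0.5 = 30 kg
- 0.3 mg/kg: 15/0.3 = 50 kg
- 0.15 mg/kg: 15/0.15 = 100 kg

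**Amount given** = min(step × weight, 15 mg). **Size of a 0.5-to-0.3 reduction** = 1 − (amount at 0.3)/(amount at 0.5).

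| Weight (kg) | 0.15 step (mg) | 0.3 step (mg) | 0.5 step (mg) | mg/kg received at 0.5 step | Reduction 0.5 to 0.3 |
|---|---|---|---|---|---|
| 20 | 3.0 | 6.0 | 10.0 | 0.500 | 40% |
| 30 | 4.5 | 9.0 | 15.0 | 0.500 | 40% |
| 35 | 5.25 | 10.5 | 15.0 | 0.429 | 30% |
| 40 | 6.0 | 12.0 | 15.0 | 0.375 | 20% |
| 45 | 6.75 | 13.5 | 15.0 | 0.333 | 10% |
| 50 | 7.5 | 15.0 | 15.0 | 0.300 | 0% |
| 60 | 9.0 | 15.0 | 15.0 | 0.250 | 0% |

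**The rules applied to a 60 kg child whose urine volume stays insufficient through Day 6.**

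1. Days 5 and 6, nominal 0.3: 0.3 × 60 = 18, capped to 15 mg.
2. Day 7, directed increase to nominal 0.5: 0.5 × 60 = 30, capped to 15 mg. The amount is unchanged.
3. If the dose is then reduced one step, the child goes to nominal 0.3, which is again 15 mg.
4. The first step that gives less is 0.15 (9 mg). Taken after step 3, it is a further reduction, which 3.2.3 treats as grounds for withdrawal. Taken directly, it is two steps down, which 3.8.3.1 item 6 treats as grounds for discontinuation.
5. Without a reduction, the evaluation dose is classed as 0.5 mg/kg; the child receives 15/60 = 0.25 mg/kg. A reduction before three days are complete changes the class to 0.3, and the child still receives 0.25 mg/kg.

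**The case against.** Several objections have force.

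- **Protection remains.** A reader might infer that these children have no safeguard. The documents do not support that. Section 3.8.3.1 stops treatment for excessive aquaresis, for the stated sodium rises, for sodium above 145 mEq/L, for adverse events and on the investigator's judgement. Reduction under 3.2.3 is also discretionary. What is lost is the option of staying in the trial on a smaller amount.
- **The wording can be read otherwise.** A site could hold that 15 mg is not lower than 15 mg and look further down the steps. That reading meets the two-step rule in 3.8.3.1, so it does not resolve the gap.
- **The scenario is narrow.** A reduction from nominal 0.5 concerns a child of at least 50 kg, under 15, normally with insufficient urine volume on all of Days 1 to 6, who then has a safety concern on the same 15 mg. This limits the size of the problem, not its existence.
- **A cap always compresses the top steps.** The narrowing between 30 and 50 kg is a consequence of the design and not in itself an error. The omission is that the step rules take no account of it.
- **Figures 3.1-1 and 3.2.4-1 could not be read here.** The second gives examples of dose reduction and might contain a note on capped subjects.

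A reader might also see a contradiction with section 2.2, which says "It is unlikely that tolvaptan therapy will pose safety issues when its maximum dose is set at 30 mg/day". That sentence goes on to equate 30 mg with 0.5 mg/kg/day in children, so it uses an adult conversion to support a mg/kg ceiling. The same section calls 15 mg/day sufficient in adults. A mg/kg ceiling and an absolute cap can coexist.

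**Conclusion.** The point holds. From 50 kg the 0.3 and 0.5 mg/kg steps are the same 15 mg. Followed as written, the Day 7 increase and the one permitted reduction from nominal 0.5 do not change the amount given. The dose label then overstates what the child received. The difference between the two steps is already reduced for any child above 30 kg.

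The arithmetic is exact and needs no assumption. The number of children affected does: the documents give no weight distribution. If only the 7 to under 15 years group can reach 50 kg, the range is 0 to 24 of 60, probably near the low end, and only some of those would reach nominal 0.5. The conclusion is also subject to the two unread figures.

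Two further inferences do not follow:

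- **Duration.** Counting 2 days at nominal 0.3, then 3 and 4 at nominal 0.5, gives 2 + 3 + 4 = 9 days on 15 mg. This does not breach the seven-day limit in 3.2.4, which counts days at the decided step: 3 + 4 = 7. Total treatment also stays within the 13 days of 3.2.5.
- **Timing of the primary endpoint.** The third day at nominal 0.5 is the fifth day on 15 mg (2 + 3), but this does not invalidate the endpoint. Its baseline is Day 1 for every child, so it already spans different treatment lengths by design.

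**What to change.** **Protocol.** Reconcile the cap in 3.2.1 with 3.2.2, 3.2.3, 3.8.3.1 item 6 and the evaluation-dose definition in 7.4, and carry the result into SAP 3.2 and 5.7. The documents should say what an increase, a reduction and a two-step reduction mean when the adjacent step is the same administered amount. The clinical rule is for the sponsor to set.

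**SAP.** Keep the primary endpoint definition and timing as they are. Restarting the three-day count from the first day on 15 mg would move the assessment from Day 10 to Day 8. It would also replace the urine volumes of Days 7 to 9 with those of Days 5 to 7, two of which were already judged insufficient, and would pre-empt the sponsor's rule. Instead, add a supplementary by-dose summary of efficacy, safety and PK by the amount actually given (mg/kg received), flagging subjects at the 15 mg cap.

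**Cost.** A short clarification and a few extra tables. Section 3.2.1 already requires the dose to be recorded in the CRF, and the pretreatment weight is measured, so no additional subjects, visits or samples are needed.

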3.2.2 Increasing the Dose of Tolvaptan

Tolvaptan should be administered according to the following procedure. Daily urine volume should be assessed as “insufficient increase in urine volume” when it is less than 150% of that for the pretreatment observation period (1 day before start of tolvaptan administration), and “sufficient increase in urine volume” when it is at least 150%.

- 1) Tolvaptan administration will be started at 0.05 mg/kg/day, and administration at 0.05 mg/kg/day will be continued for 2 days.
- 2) For subjects with sufficient increase in urine volume on Day 1 or Day 2 of treatment, administration at 0.05 mg/kg/day will be continued for 3 days. For subjects with an insufficient increase in urine volume on Day 1 and Day 2 of treatment, the dose will be increased to 0.15 mg/kg/day on Day 3.
- 3) If a sufficient increase in urine volume is observed following 2-day administration at 0.15 mg/kg/day on Day 3 or Day 4 of the treatment period, administration at 0.15 mg/kg/day will be continued for 3 days. For subjects with an insufficient

increase in urine volume on Day 3 and Day 4 of the treatment period, the dose will be increased to 0.3 mg/kg/day on Day 5.

- 4) If a sufficient increase in urine volume is observed following 2-day administration at 0.3 mg/kg/day on Day 5 or Day 6 of the treatment period, administration at 0.3 mg/kg/day will be continued for 3 days. For subjects with an insufficient increase in urine volume on Day 5 and Day 6 of the treatment period, the dose will be increased to 0.5 mg/kg/day on Day 7, and administration at 0.5 mg/kg/day will be continued for 3 days.

3.2.3 Reducing the Dose of Tolvaptan

If symptoms associated with excessive aquaresis such as persistent sensation of thirst, dehydration, and hypernatremia are observed or there are safety concerns in subjects, at a discretion of the investigator or subinvestigator, the dose may be reduced only to the next lower dose. In that case, however, the dose of conventional diuretics should not be changed. If the dose of tolvaptan needs to be reduced before completion of 3-day administration at the same dose, it should be administered at the reduced dose for 3 days. If the dose of tolvaptan needs to be further reduced after dose reduction to the next lower dose, the subject will be judged to have a problem with tolerability to tolvaptan and should be withdrawn from the trial.

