3.7.1.3.1 Day 1 of Treatment Period

The investigator or subinvestigator will perform the following procedures.

1) Before tolvaptan administration

The investigator or subinvestigator will perform the following examinations, and then, offer breakfast to the subject.

- Body weight
- Serum or blood sodium concentration
- Serum or blood potassium concentration

The investigator or subinvestigator will instruct the subject to completely discharge the urine immediately after breakfast, and start urine collection and fluid intake measurement to assess the following items.

- Daily urine volume
- Daily fluid intake

- Daily fluid balance
- Urine sodium excretion
- Urine potassium excretion
- Urine osmolality

2) Tolvaptan administration

The investigator or subinvestigator will instruct the subject to take tolvaptan (0.05 mg/kg/day) with water after breakfast. After administration, the change in serum or blood sodium concentration will be observed. If the change meets the following criteria, the investigator or subinvestigator should discontinue treatment with tolvaptan as specified in [Section 3.8.3.1](#), and perform the withdrawal examination according to [Section 3.7.1.6](#).

- Serum or blood sodium concentration increased by ≥ 8 mEq/L from that immediately before tolvaptan administration, within 8 to 12 hours after administration
- Serum or blood sodium concentration increased by ≥ 12 mEq/L from that immediately before tolvaptan administration, within 24 hours after administration
- Serum or blood sodium concentration exceeding 145 mEq/L is observed during the treatment period

3) 4 to 6 hours after tolvaptan administration

- Serum or blood sodium concentration

4) 8 to 12 hours after tolvaptan administration

- Serum or blood sodium concentration

5) At a feasible time

- Vital signs
- Edematous symptoms (after tolvaptan administration)
- Concomitant drugs and therapies
- IMP compliance
- Adverse events

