3.8.3 Individual Subject Discontinuation

3.8.3.1 Treatment Discontinuation

Treatment with the IMP should be discontinued, and the withdrawal examination specified in [Section 3.7.1.6](#) should be performed, in the cases listed below. Each investigator or subinvestigator will comprehensively review the circumstances and record the date and reason of discontinuation in a source document and a CRF.

- 1) Legal representative or subject requests to be withdrawn
- 2) After start of IMP administration, a deviation from the inclusion or exclusion criteria is discovered for the subject
- 3) Continuation of treatment is deemed unfeasible due to the occurrence of AEs
- 4) Any of the prohibited concomitant medications are used
- 5) The dose and regimen of restricted concomitant medication were changed within 24 hours before and after start of IMP administration

- 6) Excessive aquaresis is observed, or dose reduction to ≥ 2 dose steps lower is required due to concerns regarding the safety of the subject
- 7) Liver function test value (AST or ALT) increased by ≥ 3 times the upper limit of the reference range for the subject's age and gender
- 8) Serum or blood sodium concentration increased by ≥ 12 mEq/L from that immediately before IMP administration, within 24 hours after administration
- 9) Serum or blood sodium concentration increased by ≥ 8 mEq/L from that immediately before IMP administration, within 8 to 12 hours after administration
- 10) Serum or blood sodium concentration exceeding 145 mEq/L is observed during the treatment period
- 11) Serum or blood potassium concentration exceeds the upper limit of the reference range for the subject's age and gender during the treatment period
- 12) Subject's pregnancy is confirmed or suspected
- 13) The investigator or subinvestigator judges that withdrawal is necessary for any other reasons

After start of treatment with the IMP, a subject may stop treatment permanently for a variety of reasons. Treatment discontinuations may be initiated by a subject who is not satisfied with treatment, when medically necessary due to AEs, when requiring treatment with a disallowed medication or therapy, or other issues, as determined by the investigator. However, options for continued treatment should be offered to the legal representative or subject to the degree possible as described in [Section 3.8.3.4](#).

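### Protocol 3.2.3 allows a dose reduction for hypernatremia, while 3.8.3.1 item 10 calls for stopping above 145 mEq/L, and no available text says which prevails

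*Protocol*

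**What the plan says.** **Reduction.** Protocol 3.2.1 introduces the option: "If the investigator or subinvestigator judges that there are an excessive aquaresis or safety concerns of subjects, the dose may be reduced". Section 3.2.3 gives the triggers, "If symptoms associated with excessive aquaresis such as persistent sensation of thirst, dehydration, and hypernatremia are observed" or other safety concerns, and leaves a single step down to the investigator's discretion. If the child has not completed 3 days at the dose, "it should be administered at the reduced dose for 3 days". SAP 3.2.1 and 3.2.3 repeat these rules.

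**Limits on reduction.** Section 3.2.4 adds: "If the dose needs to be reduced before completion of 3-day administration, the dose may be reduced only once". Section 3.2.3 covers the next event: "If the dose of tolvaptan needs to be further reduced after dose reduction to the next lower dose", the child is withdrawn.

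**Stopping.** Protocol 3.8.3.1 lists the cases in which treatment should be discontinued. Item 10 is "Serum or blood sodium concentration exceeding 145 mEq/L is observed during the treatment period". The Day 1 procedures (3.7.1.3.1) repeat the sodium criteria and say that "the investigator or subinvestigator should discontinue treatment with tolvaptan" when one is met.

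**Cut-off.** Exclusion criterion 5 in Protocol 3.4.3 equates hypernatremia with sodium above 145 mEq/L. Section 3.2.3 gives no sodium value of its own.

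**The concern.** Two operative rules attach different actions to what the protocol's own cut-off makes the same finding. Two sites could act differently on the same result, each citing the protocol. A child reduced under 3.2.3 could also be counted under SAP 7.6 in the deviation class for subjects who met a withdrawal criterion but stayed on treatment.

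This is a sodium-safety instruction in a trial that admits children too young to complain of thirst. The protocol's rationale for inclusion criterion 3 itself warns that sodium may rise rapidly with excessive diuresis. There is an analysis consequence too: dose and regimen are part of the primary objective, results are tabulated by evaluation dose, and the action taken can determine that dose.

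**Working it through.** **1. Do the rules overlap?** The stop rule applies above 145 mEq/L. The only numerical cut-off for hypernatremia is also above 145 mEq/L. If 3.2.3 uses the word in that sense, every hypernatremia that permits reduction also meets item 10. The reduced-dose provisions (3.2.4 and 3.7.1.5) contain no sodium exception, and neither 3.2.3 nor 3.8.3.1 refers to the other on this point.

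**2. Which children are affected?**
- At 0.05 mg/kg/day there is no lower step, so only stopping is possible.
- A child already reduced once who needs a further reduction is withdrawn under 3.2.3 itself.
- That leaves a child at 0.15, 0.3 or 0.5 mg/kg/day who has not yet been reduced.

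**3. Does the action change the analysis?** It does if the event comes before 3 days at the dose and either after a sufficient urine increase or at 0.5 mg/kg/day (SAP 5.7, criterion 1). After 3 full days, a reduction leaves the evaluation dose unchanged. Example: 0.05 mg/kg/day on Days 1–2, 0.15 on Day 3 with a sufficient urine increase, sodium above 145 mEq/L before breakfast on Day 4.

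| | Reduced, 3 days completed | Stopped |
|---|---|---|
| Dosing | 0.05 on Days 4–6 | last dose on Day 3 |
| Evaluation dose (SAP 5.7) | 0.05 | 0.15 |
| Weight for the primary endpoint | Day 7 | Day 4, carried forward (SAP 5.6) |
| Completer (Protocol 3.10) | yes | no |
| Dose maintenance set (SAP 5.2) | yes | no |

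On the stopped path the target weight would be the day after a third day at 0.15 (Days 3, 4, 5), which is Day 6. Follow-up falls 5 to 7 days after the last dose, on Days 8–10, so Day 4 is the last scheduled weight by Day 6. Responder status may or may not differ between the two paths.

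**4. A related gap.** Suppose the child had no sufficient urine increase, was reduced at 0.15 or 0.3, and completed 3 days. SAP 5.7 criterion 1 needs a sufficient increase during escalation or escalation to 0.5; criterion 2 needs discontinuation. Neither fits. Protocol 3.2.4 says "The reduced dose should be regarded as the dose decided for each individual subject", but SAP 5.7 does not tie that status to the evaluation dose. It also omits the sentence in Protocol 7.4 that leaves room for other definitions.

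**5. Size on the primary proportion.** Assume all 60 planned subjects are in the full analysis set.
- One child: 1/60 = 1.67 percentage points.
- Exact 95% lower limit for k responders: the 0.025 quantile of Beta(k, 60 − k + 1).
- k = 25 (41.7%): Beta(25, 36) gives 0.291.
- k = 26 (43.3%): Beta(26, 35) gives 0.306.

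The planning threshold of 0.3 lies between these two limits, so one child decides the comparison only at that boundary.

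**The case against.** The strongest reply is that the documents already lean one way. Item 10 is specific and says *should*; 3.2.3 is general and says *may*, with no exemption from 3.8.3.1. The Day 1 text repeats the stop with no reduction option, and SAP 7.6 treats unheeded withdrawal criteria as serious deviations. A site reading both sections might well stop. That is a fair inference, but it is not a stated precedence, and under the protocol's own cut-off it would leave the word hypernatremia in 3.2.3 with no effect. The Day 1 text governs dosing at 0.05 mg/kg/day, where the conflict cannot arise.

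Three further points stand as limits:
- The 145 mEq/L meaning is taken from an eligibility criterion. Section 3.2.3 could intend something else, though nothing in it says so.
- Figure 3.2.4-1, which is said to give examples of reduction, is not shown in the text available for review and could not be checked.
- SAP 5.7 and 6.1 do not say whether the earlier days at 0.05 count toward the third day. Counting Days 1, 2 and 4 would put the weight on Day 5. The fresh 3-day course in 3.2.3 and the reduced-dose schedule in 3.7.1.5 support Day 7.

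The SAP 5.7 gap is separable: it arises for any reduction before a sufficient urine increase, whatever the trigger. SAP section 14 does not list the flexibility sentence in Protocol 7.4 as withdrawn, so the gap is in the SAP's wording and is not proof that such a child could not be handled.

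**Conclusion.** The concern holds. For a child above 0.05 mg/kg/day who has not yet been reduced, the documents attach both a discretionary reduction and a discontinuation to sodium above 145 mEq/L, and no available passage ranks them. This rests on reading hypernatremia in 3.2.3 by the protocol's only stated cut-off. It does not depend on the SAP 5.7 gap or on the boundary calculation.

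The effect on the primary estimate is probably secondary and cannot be sized in total, because no incidence of sodium above 145 mEq/L is given. The contradiction should be fixed because it concerns a safety instruction for children. No view is taken here on which clinical rule is right.

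**What to change.** - Reconcile Protocol 3.2.1, 3.2.3, 3.7.1.3.1 and 3.8.3.1 item 10, together with SAP 3.2.1 and 3.2.3, so that a given sodium finding leads to one stated action or one rule is stated to take precedence. The sponsor decides which.
- Apply the SAP 7.6 deviation class consistently with that decision.
- Clarify 3.8.3.1 item 6 at the same time: excessive aquaresis is listed there as a reason to stop, and in 3.2.1 and 3.2.3 as a reason to reduce.
- If reduction remains possible before a sufficient urine increase, add a line to SAP 5.7 naming the evaluation dose for a child reduced at 0.15 or 0.3 who then completes 3 days.

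The cost is one or two sentences in the protocol, the same in the SAP, and one line in SAP 5.7. No new data or patients are needed.
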